### 3.2 Study measures and outcomes

Table 1: Measures and Timing

Variable (source) # = adolescent, * = parent	T0: Enrollment	T1: End of Intervention	T2: 4-week Follow up
Demographics##	X		
PROMIS Pediatric Global Health 7+2 or Parent Proxy Global Health 7+2#	X	X	X
PROMIS Pediatric Pain Interference or Parent Proxy Pain Interference#	X	X	X
Parent: (physical and emotional) PROMIS 29 Symptom Profile*	X	X	X
Hair Sample Collection##	X		X
Parent Experience of Providing Reiki*			X
Saliva collection##	Pre/post 2 Reiki sessions per week during weeks 1-4		
Medication Log#	Completed during weeks 0-4		
Parent intervention Log*	Completed during weeks 1-4		

Demographic form (T0) basic demographic information on both parent and adolescent.

Patient Reported Outcomes Measurement Information System (PROMIS), sponsored by the NIH. *PROMIS Pediatric Pain Interference* or *PROMIS Parent Proxy SF Pain Interference*, assesses how pain interferes with daily life for the adolescent. Well-validated measures show significant correlations between child and parent reports of pain. We will use the *PROMIS Pediatric Global Health 7+2* measure to obtain an overall evaluation score of the adolescents' physical and mental health. Both self-report and parent proxy versions are valid and reliable. Adult profile PROMIS 29 Symptom Profile (parent) assesses seven domains (depression, anxiety, physical function, pain interference, fatigue, sleep disturbance and ability to participate in social roles and activities).

Medication Log documenting all pain medications given one week prior to and during the intervention period.

Parent Intervention Log provided for parent record keeping. These logs will document Reiki session details, including the date, time, and length of session, interruptions to session, where the session took place, and parent comments and reactions (including adolescent reactions).

Hair collection and assay: Hair cortisol concentration (HCC) is a measure of chronic stress. A recent study found that the mean cortisol level assayed in 1 cm of hair was correlated ( $r=0.61$ ,  $p<0.01$ ) with the mean

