The primary outcome for the proposed study is the feasibility and acceptability of teaching Reiki to parents of adolescents receiving palliative care. Secondary outcomes include: adolescent global health, pain interference, medication use, and stress measures of hair cortisol (chronic, long term) and alpha amylase (immediate, short term); and parent symptom profile (depression, anxiety, physical function, pain interference, fatigue, sleep disturbance and ability to participate in social roles and activities), and stress measures of hair cortisol (chronic, long term) and alpha amylase (immediate, short term).

Because Reiki has not been taught to parents of adolescents receiving palliative care at home, we will determine the feasibility and acceptability of this intervention through calculating the percentage of dyads approached to the total participants who consented to participate in the study as well as completed the study. We will also conduct qualitative interviews with parents to examine what they thought of the teaching protocol, the usefulness of Reiki for stress and other symptoms, as well as their thoughts on the study as a whole. Secondary outcomes will be collected in order to explore preliminary evidence on overall health and quality of life as well as medication use for the adolescents and overall quality of life and symptoms of the parent.

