### **3.2.1 Study events description**

Dyads will be in the study for a total of nine weeks from enrollment to the follow-up visit. Screening occurs at least weekly and prior to enrollment. Enrollment and initial study measure completion, including first hair sample collection from both parent and adolescent, will occur at the beginning of Week 0. Parents will fill out the Medication Log during Week 0 in order to have a baseline of pain and anxiety medications before study intervention begins. The parent will receive Reiki training, a poster with suggested hand positions and a commercially-available book about Reiki in the home on the first day of Week 1. A visit window is defined as a week (7days) -1/+3 days from the initial Reiki training. During Week 2 the parent will receive a Reiki booster session with a repeat of the training and may ask questions. The parent will administer at least 5 times per week for at least 10 minutes each session. During weeks 1-4, the parent will collect saliva samples for themselves and their adolescent before and after any two Reiki sessions as long as they are collected on two separate days. At the end of Week 4, measures will be repeated either in person or by phone. During Week 8, measures will be repeated, the second hair sample obtained from both parent and adolescent, and the parent will participate in a qualitative interview. The qualitative interview will be administered in person by trained OSU College of Nursing

study staff as part of the interview session. Interviews will be audio recorded using a hand-held audio recording device. Audio recordings will be transcribed verbatim. Audio recording is voluntary and participants can choose to not have their interview recorded and still be a part of the study. See Appendix 2 for schema.

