## **3.3 Interventions**

This is a one-group feasibility study. There is only one intervention group. The Overall-Study PI and Local PI will recruit professional Reiki practitioners who are trained at Level 3 or Master Level and have prior experience working with families and children. A Reiki Master will perform the initial teaching and instruct the parent how to perform a simple 15-minute Reiki session. Parents will complete a return demonstration using light touch with their adolescent. The parent will receive an introductory book on Reiki, an informational article, and a poster showing hand positions for their reference as well as the intervention log to record sessions. The initial teaching session will take about 1.5 hours with breaks. The initial teaching session will be conducted by a Reiki Master and will mark the beginning of Week 1. A Reiki practitioner (Master or Level 3) will provide a shorter "booster" session the following week to review techniques with the parent and answer questions. This session will last 45 minutes with breaks. The "booster" session will count as one day for that week. Parents will be asked

to complete a minimum of 15 minutes of Reiki with their adolescent at least five days per week for the four-week intervention period. Parents will receive a phone call from the research coordinator once per week during weeks three and four to check in with them and ask if they have any questions or problems with the intervention and will refer to a Reiki practitioner if needed.

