## 4 Statistics and Data Handling

### 4.1 Statistical considerations

Primary outcomes (Aims 1): Feasibility will be examined by computing the proportion of approached subjects enrolled in the study, the proportion of subjects who complete Reiki training, and the proportion of enrolled subjects' who completed data collection. Qualitative data will be analyzed using a basic qualitative descriptive approach. Qualitative data (audio recorded interviews and field notes) will be transcribed verbatim, checked for accuracy, imported into Atlas.TI for data management, and analyzed. Portions of text are labeled or coded with terms that are descriptive of the user opinions and observations. Codes will be identified and defined in an iterative process by investigators independently coding the data and arriving at agreement in discussion/review. Codes are sorted and categorized into themes, which will be discussed in research meetings. We will use mixed methods to triangulate the qualitative and quantitative data to produce a more accurate picture of parental beliefs and experiences. These results will be used to refine procedures for future, larger studies. Qualitative results will be triangulated with quantitative results to answer questions of feasibility. Qualitative results will also be examined to explore the parents' confidence in delivering Reiki and beliefs in their ability to help their adolescent (Aim 3).

Secondary outcomes (Aim 2): Descriptive statistics will be used to check data distribution, identify outliers, examine the balance in baseline measurements, and report outcome measures (e.g. pain) at each time point. Trend plot will be used to visualize the trend of change over time. Pair-wise comparisons will be conducted to test the difference in the change in outcome measures (T0 versus T1, T1 versus T2, T0 versus T2) using two sample t-tests. We will not adjust for multiple comparisons to avoid further reduction of power. Mixed effect modeling for repeated measures will be used to examine the trajectories of treatment effect over time, adjusting for within-patient clustering from repeated measures and possible confounders.

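### Medication use is logged only in Weeks 0-4, so two of the three planned contrasts have no data and the third applies an unpaired test to undefined values

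*Combined protocol and SAP*

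**What the plan says.** **Status.** The synopsis and section 3.2 both list the outcome: "Secondary outcomes include: adolescent global health, pain interference, medication use, and stress measures of hair cortisol".

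**When it is recorded.** In Table 1 (section 3.2) the Medication Log row reads "Completed during weeks 0-4", with nothing at the 4-week follow-up. Section 3.2.1 explains the first week: "Parents will fill out the Medication Log during Week 0 in order to have a baseline of pain and anxiety medications before study intervention begins". Section 3.3 sets the Reiki schedule "at least five days per week for the four-week intervention period", so the log covers one week before and four weeks during the intervention.

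**When T0, T1 and T2 fall.** Sections 3.2.1 and 3.2.2 place T0 at enrollment (the start of Week 0), T1 at the end of the intervention in Week 4, and T2 in Week 8.

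**How it is analysed.** For the Aim 2 outcomes, section 4.1 plans pairwise comparisons to "test the difference in the change in outcome measures (T0 versus T1, T1 versus T2, T0 versus T2") and names two-sample t-tests. It also plans descriptive summaries, a plot of trends and a repeated-measures mixed model. It gives medication use no rule of its own.

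**What counts as medication.** Section 3.2 refers to a "Medication Log documenting all pain medications given one week prior to and during the intervention period". Section 3.2.1 gives the purpose as "in order to have a baseline of pain and anxiety medications before study intervention begins". Section 3.2.3 and the title of the form in Appendix 3 also cover both pain and anxiety medicines.

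**The concern.** The contrasts in section 4.1 suit questionnaires completed at three visits. Medication use is a running log that ends at T1, so the stated analysis does not fit it. There are three consequences.

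- Two contrasts have no data.
- The remaining contrast is a before/after comparison in one group, but the named test assumes two independent samples.
- The variable being tested is not defined. The log has only just been opened at T0, so a T0 value must be built from the week that follows. A T1 value could be Week 4 alone or all of Weeks 1-4.

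Section 4.1.1 says that preliminary primary and secondary results will inform the size of a later randomized trial. A result that depends on choices of period, unit and medicine class made after the data are seen is a weak basis for that, and with 12 dyads such choices can weigh heavily.

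**Working it through.** The plan gives no figure for this outcome that could be reproduced. The check is a count of usable contrasts, a look at the test, and simple ratios.

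**Inputs.** Week 0 is 7 days nominal (section 3.2.1). The intervention is 4 weeks, or 28 days (section 3.3). T0, T1 and T2 are as in section 3.2.2. The sample is 12 dyads (section 4.1.1).

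**1. Timeline.** 1 + 4 + 4 = 9 weeks, which matches the stated nine weeks. The log covers 1 + 4 = 5 of them and has no entries in Weeks 5-8.

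**2. Contrasts.**
- T0 v T1: both ends lie within the log period, but neither value is defined.
- T1 v T2: no T2 value.
- T0 v T2: no T2 value.

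Two of the three cannot be run.

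**3. The test for the contrast that remains.** Take n adolescents with equal standard deviation σ at both times and within-person correlation ρ.
- Two-sample standard error: σ√(2/n).
- Correct standard error of the within-person difference: σ√(2(1−ρ)/n).
- Ratio, correct to two-sample: √(1−ρ).

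If ρ is positive, the two-sample test overstates the error and loses power. If all 12 adolescents contribute, it treats 24 values as independent (24 − 2 = 22 degrees of freedom) when there are 12 pairs (12 − 1 = 11). The documents give no ρ, so the loss is not quantified here.

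**4. If raw totals were compared (conditional).** With daily rates r₀ in Week 0 and r₁ in Weeks 1-4, the ratio of totals is 28r₁ / 7r₀ = 4 × (r₁/r₀).
- Unchanged use, r₁/r₀ = 1: ratio 4.00.
- Use halved, r₁/r₀ = 0.5: ratio 2.00, so a true fall reads as a doubling.
- Equal totals need r₁/r₀ = 7/28 = 0.25, a 75% fall.

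Per day, the three ratios are 1.00, 0.50 and 0.25, as they should be.

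**5. Which denominator.** Section 3.2.3 has staff ask about a blank log, which accepts that blank can mean none given. As an illustration, let use go from 2 administrations a day on 7 days to 2 a day on 3 days of a week.
- Per day with an entry: 14/7 = 2 against 6/3 = 2, no change.
- Per calendar day covered: 14/7 = 2 against 6/7 = 0.86, a fall of 1 − 6/14 = 57%.

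Calendar days covered by the log are therefore the right denominator.

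**The case against.** The strongest reply is that section 4.1 offers more than the t-tests. The trend plot and the mixed model could take weekly values from Weeks 0-4, and Table 1 already shows that the log stops, so a sensible analyst would simply not run the T2 contrasts. Much of this stands. A reader might infer that the plan has no means of analysing medication use, and the documents do not support that. Only the two T2 contrasts are impossible. What remains is that no weekly variable is defined for the plot or model, and that the stated test does not match the one-group design.

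A reader might also infer that the planned analysis will show a fourfold rise. No section says that a 7-day total will be set against a 28-day total, so the factor of 4 shows what an undefined period allows and is not a result of the plan.

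A third tempting reading is that the log records no usable unit. The form's columns do not appear in the text available for this review, so it may capture drug, dose and time. The supportable statement is that sections 3.2 and 4.1 name no summary measure.

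Finally, section 4.1.1 puts the emphasis on Aims 1 and 3, and no success or stopping criterion rests on medication use. That is correct, and it limits the severity.

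**Conclusion.** The point holds as a mismatch between one named secondary outcome and its stated analysis. Two of three contrasts have no data. The third would treat before and after values from the same adolescents as independent, and its T0 and T1 values are undefined. These statements rest on the documents alone. The factor of 4 assumes nominal weeks, constant daily use and a comparison of raw totals, and the last of these is not stated in the plan.

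The scope conflict between pain medicines (section 3.2) and pain and anxiety medicines (sections 3.2.1 and 3.2.3, Appendix 3) would be clerical on its own, but it decides what the outcome contains.

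Severity is minor to moderate. Medication use is an exploratory Aim 2 outcome in a 12-dyad feasibility study, and the primary outcome is untouched.

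**What to change.** In section 4.1, add a short paragraph for medication use:

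- **Variable.** Rate per calendar day covered by the log, reported by medicine class. Count confirmed non-use as zero, and treat days neither entered nor confirmed as missing.
- **Comparison.** Week 0 against Week 4 within person, by a paired test chosen in advance. The periods are nominally equal in length, and the per-day rate absorbs small differences.
- **Course over time.** Weekly values from Weeks 0-4 in the trend plot and mixed model already planned, so that Weeks 1-3 are used.
- **Exclusion.** State that T1 v T2 and T0 v T2 do not apply to medication use.
- **Limitation.** State that counts of administrations are sensitive to a switch between medicines with different dosing frequency. Reporting by class does not remove this when the switch is within a class.

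Reconcile the log's scope in section 3.2 with sections 3.2.1 and 3.2.3 and Appendix 3.

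The cost is protocol and analysis wording only. The change uses the log already collected and adds no visit, form or burden for families.

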salivary cortisol. A four-week follow-up period was chosen in order to obtain an accurate measure of HCC to determine any change in stress during the intervention period. Approximately 10-75 mg of hair is cut from the posterior vertex region of the scalp as close to the scalp as possible. The posterior vertex has the lowest variation in cortisol levels, and is the preferred area for sampling. Co-I ([name]) will train the PI and Co-I ([name]) on hair collection. We will take one cut at the first home visit (T0) and another at the four-week follow-up home visit (T2). Assay: Each 1 cm of hair approximates the mean cortisol level over the prior 1 month. Samples are assayed in duplicate and inter- and intra-assay coefficients of variation calculated. HCC levels are expressed in hair as pg/mg.

Saliva collection and assay: Salivary alpha amylase (sAA) is a non-invasive biomarker that detects immediate changes in autonomic nervous system response, signaling a change in level of stress. Interventional studies have shown a decrease in sAA levels as a response to an intervention meant to stimulate relaxation. Collection: The Salimetrics Drool Tube for adults will be used for saliva collection from the parents and cognitively aware adolescents. The SalivaBio Swab for infants will be used for the remaining adolescents to eliminate any choking hazards. Samples will be collected for both parent and adolescent pre and post two Reiki sessions per week for four weeks. Storage: The swab will be placed in a Swab Storage Tube. Tubes will be put into a sealable plastic bag marked as parent or adolescent, the date and time of collection, and put into the home freezer until the PI or other team member collects them at the follow up visit. Samples will be transported on dry ice to the lab, and frozen at -20C until processed. Assay: The saliva samples will be batch processed after thawing using the Salimetric Alpha Amylase assay following manufacturer's instructions. The amount of alpha-amylase activity present in the saliva sample is directly proportional to the increase in absorbance at 405 nm.

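### The plan does not say which hair segment is assayed at Week 8, so that cortisol value may not reflect Weeks 1-4; corticosteroid use after entry is only partly captured

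*Combined protocol and SAP*

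**What the plan says.** Hair is cut from parent and adolescent at enrolment (T0, start of Week 0) and at the Week 8 visit (T2), with no cut at the end of the intervention (T1). Section 3.2 gives the purpose of the four-week follow-up as to "obtain an accurate measure of HCC to determine any change in stress during the intervention period".

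The collection text says the hair "is cut from the posterior vertex region of the scalp as close to the scalp as possible", with the amount given as "Approximately 10-75 mg of hair". On the assay it says "Samples are assayed in duplicate and inter- and intra-assay coefficients of variation calculated", and results are in pg/mg. Length appears in two statements: "Each 1 cm of hair approximates the mean cortisol level over the prior 1 month", and a cited study in which "the mean cortisol level assayed in 1 cm of hair was correlated" with salivary cortisol. Neither is an instruction on what to assay. Section 4.1 plans T0 versus T2 comparisons without defining an HCC segment.

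Section 3.1.1 excludes dyads if either member has less than one inch of hair. It also excludes them for corticosteroid use in the last 30 days, because this affects HCC. After entry, the medication record is the adolescent's log for Weeks 0-4. Section 3.2 describes it as covering pain medicines; section 3.2.1, section 3.2.3 and the form's title in Appendix 3 add anxiety medicines.

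**The concern.** A hair segment is a calendar record, so its position on the strand decides which weeks it describes. At T2 the hair next to the scalp was formed after the intervention ended, apart from any delay between exposure and the cut end. Without a stated segment, the T0-T2 change could reflect follow-up stress, or a mixture of periods, and still be reported as change during the intervention.

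Corticosteroids raise a second problem. The protocol recognises them as a disturbance of HCC and screens for them once. A course started later by either person could shift the T2 value and would look like a change in stress. With 12 dyads, one such course could visibly move the summary. Section 4.1.1 says the preliminary primary and secondary results will inform the sample size of the next trial.

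**Working it through.** The plan gives no figure to reproduce, so the check is a calendar overlap.

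**Inputs**
- Day 0 is the start of Week 0 (section 3.2.1).
- Training is on the first day of Week 1 and the intervention lasts four weeks (sections 3.2.1 and 3.3), so it occupies days 7 up to 35: 28 days.
- T2 is in Week 8, days 56-62. Section 3.2.1 states "A visit window is defined as a week (7days) -1/+3 days from the initial Reiki training". Applying -1/+3 days to Week 8 is an assumption and gives days 55-65.
- Days per cm, r: one month, taken as 28 to 30.4 days.
- Delay, d: none is stated. I use 0, and 14 days as an assumed alternative.
- One inch is 2.54 cm.

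**Formula.** A segment from s to e cm from the cut end covers days T2 - d - e×r up to T2 - d - s×r. Its intervention share is the overlap with days 7 to 35 divided by (e - s)×r.

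**Extremes with no delay**
- 0-1 cm, highest: T2 = 55, r = 30.4 covers days 24.6-55; (35 - 24.6)/30.4 = 10.4/30.4 = 34%. Lowest: T2 = 65, r = 28 covers days 37-65; 0%.
- 1-2 cm, lowest: T2 = 55, r = 30.4 covers days -5.8 to 24.6; (24.6 - 7)/30.4 = 17.6/30.4 = 58%. Highest: T2 = 63, r = 28 covers days 7-35; 100%.
- Whole inch: all 28 days fall inside it; 28/(2.54×30.4) = 36% to 28/(2.54×28) = 39%.

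**Extremes with an assumed 14-day delay**
- 0-1 cm: T2 = 65, r = 28 covers days 23-51; 12/28 = 43%. T2 = 55, r = 30.4 covers days 10.6-41; 24.4/30.4 = 80%.
- 1-2 cm: T2 = 55, r = 30.4 covers days -19.8 to 10.6; 3.6/30.4 = 12%. T2 = 65, r = 28 covers days -5 to 23; 16/28 = 57%.

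| T2 segment | No delay | 14-day delay (assumed) |
|---|---|---|
| 0-1 cm | 0-34% | 43-80% |
| 1-2 cm | 58-100% | 12-57% |
| Whole inch, unsegmented | 36-39% | 36-39% |

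The two 1 cm segments hold equal shares when their boundary falls on day 21, the middle of the intervention: d = T2 - r - 21. Over days 55-65 this runs from 55 - 30.4 - 21 = 3.6 days to 65 - 28 - 21 = 16 days. A modest change in an unstated delay therefore reverses which segment is better.

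**Corticosteroid capture after entry, by person and period**

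| | Weeks 0-4 | After Week 4 |
|---|---|---|
| Adolescent | Only if logged as a pain or anxiety medicine | No planned record |
| Parent | No planned record | No planned record |

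**The case against.** Several points on the other side have force.

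- The four-week wait was chosen with HCC in mind and may be meant to let hair grow out. A reader might infer that the T2 timing is simply wrong. The documents do not support that: with a 14-day delay the scalp-end centimetre is 43-80% intervention time, and with no delay the 1-2 cm segment covers the period well. What stands is that the segment and the delay are both unstated.
- A reader might infer that T0 is as open as T2. It is not. The 1 cm wording and the 30-day corticosteroid look-back together point to the scalp-end 1 cm at T0, although neither says so. They do not settle T2, where the same centimetre may describe a different period from the one intended.
- A laboratory procedure outside the protocol may fix the segment, and nothing suggests that the laboratory would vary it between samples. That is fair, but the link from segment to study period belongs in the plan.
- A reader might infer that no corticosteroid use after entry is recorded. That goes too far: a corticosteroid given to the adolescent as a pain or anxiety medicine in Weeks 0-4 would be logged. The log's columns could not be read in the text available, so this rests on its title and description.
- Two T2 segments could add a second, unadjusted HCC contrast. This stands, and it is why one segment must be named in advance.

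**Conclusion.** The concern holds in limited form. The plan ties the T2 hair value to Weeks 1-4 without naming the T2 segment. Depending on the segment and the delay, intervention time makes up anywhere from 0% to 100% of a 1 cm segment, and 36-39% of an unsegmented inch. These figures assume T2 on days 55-65, 28-30.4 days per cm and a delay of 0 or 14 days. The documents confirm neither the delay nor an individual growth range. They support saying that the T2 value may not show stress during Weeks 1-4, not that it cannot.

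The corticosteroid gap holds for the parent throughout, for the adolescent after Week 4, and for the adolescent in Weeks 0-4 unless the drug is logged as a pain or anxiety medicine.

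Priority is low. HCC is one exploratory Aim 2 outcome, section 4.1.1 puts the emphasis on Aims 1 and 3, and the primary feasibility outcome is untouched. This is a cheap improvement.

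**What to change.** 1. **Corticosteroids.** At T1 and T2, ask both dyad members about any corticosteroid use since the last contact, with dates. Repeat the HCC summary without affected samples.
2. **Segments.** State that 0-1 cm from the cut end is assayed at T0. At T2, do not assay an unsegmented inch: assay 0-1 cm and, where length and mass allow, 1-2 cm separately. Record the cut date.
3. **Comparison.** Before assay, state the assumed growth rate and delay. Name the one T2 segment that then best covers Weeks 1-4 as the value for the T0-T2 comparison, and report the other descriptively. If only a segment mainly covering Weeks 5-8 is available, report it as follow-up stress and reword the purpose sentence in section 3.2.

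**Cost.** No new visit or cut is needed: one laboratory instruction and one question at two existing contacts. There are up to 12 dyads × 2 people = 24 extra duplicate assays.

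**Downsides.** Mass may be short. If a 10 mg sample is spread evenly over one inch, 10/2.54 = 3.9 mg per cm, or about 2.0 mg per duplicate; a 75 mg sample gives 29.5 and 14.8 mg. The protocol states no minimum assay mass. A haircut after entry may remove the older segment. The documents do not show that 0-1 cm at T0 and 1-2 cm at T2 are comparable across strand positions, so that contrast needs a caveat. The calendar labels are only as good as the assumed growth rate and delay.

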#### 4.1.1 Sample size

We will enroll 12 adolescent-parent dyads in order to achieve study objectives. The emphasis is on Aims 1 and 3, the feasibility and acceptability of the study as well as the parents' feelings about learning Reiki and their ability to help their adolescents. These aims will inform future study protocols. Aim 2 is exploring both parent and adolescent stress, symptoms, and overall quality of life. We are also testing data collection of hair and saliva in this population of adolescents receiving palliative care in the home. The preliminary results from the primary and secondary outcomes will inform the sample size of the next planned study, a two-group randomized controlled trial.

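### Section 4.1 fixes no analysis scale for hair cortisol or salivary amylase and no action after its distribution check; a within-person log analysis should be pre-specified and would be more precise if the values are right-skewed.

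*Combined protocol and SAP*

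**What the plan says.** Section 3.2 names hair cortisol and salivary alpha-amylase, in adolescent and parent, as secondary outcomes.

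- **Cortisol** is a concentration: "HCC levels are expressed in hair as pg/mg". Hair is cut at T0 and T2 only.
- **Amylase** is an enzyme activity: "The amount of alpha-amylase activity present in the saliva sample is directly proportional to the increase in absorbance at 405 nm". Saliva is taken before and after two Reiki sessions a week for four weeks, not at T0, T1 and T2.

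Section 4.1 treats all Aim 2 outcomes alike. Changes between T0, T1 and T2 are tested "using two sample t-tests", and "Mixed effect modeling for repeated measures will be used to examine the trajectories of treatment effect over time". Beforehand, "Descriptive statistics will be used to check data distribution, identify outliers". Nothing says what follows from that check: there is no transformation, rank method or outlier rule.

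On size, section 4.1.1 says: "We will enroll 12 adolescent-parent dyads in order to achieve study objectives". It gives no SD, effect or power for either biomarker. It puts the emphasis on Aims 1 and 3, and says that primary and secondary results will inform the sample size of the next planned study, a randomized trial.

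**The concern.** A concentration or an activity cannot be negative, and change in such a measure is often proportional rather than a fixed number of units. If the values are right-skewed, an untransformed mean change in 12 people leans on those with the highest levels and its interval is wider than it need be.

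The planned check is a weak safeguard. With 12 differences it will often miss skewness. When it does find something, the analyst must choose a transformation or drop a value with the results in view. A biomarker result could then turn on one person or on one late decision, and a raw SD inflated by one participant could carry into the sample size of the next trial.

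**Working it through.** **Plan's own figure.** There is none to reproduce. Twelve dyads are given without effect, SD, alpha or power.

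**Inputs.** From the documents: n = 12 per comparison before dropout, and two-sample t-tests. Assumed, because the documents are silent: two-sided 5%; lognormal values; one pre/post pair per person; equal log-SD s at both times, 0.4 to 1.0; log-scale correlation r of 0.5 or 0.7; a true fall of 40% or 20%. The corresponding CV is √(exp(s²) − 1), or 0.42, 0.66, 0.95 and 1.31 for s = 0.4, 0.6, 0.8 and 1.0.

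**Log-scale paired power, by formula.** The SD of the log change is s√(2(1 − r)). The noncentrality is |ln 0.6|√12 / SD on 11 degrees of freedom. For s = 0.8 and r = 0.7, SD = 0.8 × √0.6 = 0.620 and noncentrality = 0.511 × 3.464 / 0.620 = 2.86, giving 74% power. The simulation agrees.

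**Simulation.** 40,000 trials per cell, 40% fall, power on raw v log values:

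| log-SD | r | paired t, raw v log | two-sample t, raw v log |
|---|---|---|---|
| 0.4 | 0.5 | 96% v 98% | 88% v 92% |
| 0.4 | 0.7 | 99.7% v 99.9% | 91% v 95% |
| 0.6 | 0.5 | 66% v 77% | 44% v 52% |
| 0.6 | 0.7 | 84% v 93% | 45% v 54% |
| 0.8 | 0.5 | 37% v 53% | 21% v 27% |
| 0.8 | 0.7 | 53% v 74% | 19% v 24% |
| 1.0 | 0.5 | 21% v 37% | 11% v 16% |
| 1.0 | 0.7 | 31% v 55% | 9% v 11% |

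Paired gains are 0 to 2 points at log-SD 0.4 and about 9 to 24 points at 0.6 to 1.0. Two-sample gains are about 3 to 8 points. For a 20% fall, paired gains are about 4 to 8 points and two-sample gains are under 2.

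**Error rate with no true change.** The paired test rejects in about 5% on logs and 3 to 5% on raw values. The two-sample test rejects in about 1% (r 0.5) or 0.2% (r 0.7) on either scale, so logs do not repair the ignored pairing.

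**Influence of extremes.** The largest of 12 raw changes carries a median of about 40 to 50% of the sum of squares at log-SD 0.6 to 1.0, against 32% on logs. At CV 0.3 the raw share is 34%, close to normal data.

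**The distribution check.** With r = 0.6, Shapiro-Wilk on the 12 raw differences flags about 21%, 34% and 45% of trials at log-SD 0.6, 0.8 and 1.0 when nothing changes, and about 29%, 41% and 52% under the 40% fall. It misses about half or more.

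**Counter-check where the raw scale is right.** Normal data, CV 0.3, additive fall of 20% of the mean, paired test: power goes from 43%, 65% and 91% on raw values to 37%, 57% and 82% on logs, for r = 0.3, 0.6 and 0.8.

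**The case against.** The strongest reply is that the plan never commits to raw values. A reader might infer it from the pg/mg sentence, but that gives the assay's unit and is compatible with a log analysis. A distribution check could itself lead to a transformation. This stands: what the documents show is a scale left open, with untransformed values as the default reading.

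Nor do the documents support saying that one or two high values will dominate. They give no SD or skewness, and one or two values carry most of the spread only if the CV is about 1 or more.

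The larger gains belong to a paired test, which is not the one named. With two-sample tests the direction holds but the size shrinks. The 40% fall is also unsupported; at an assumed 50% fall, CV 1.0 and r 0.6, even the two-sample gain reaches 13 points (37% to 50%).

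One pair per person does not represent amylase, which has up to 2 × 4 = 8 pairs. Using them all could leave little to gain for a large fall. The T0, T1 and T2 contrasts do not cover these samples at all.

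Finally, Aim 2 is exploratory and no biomarker result can alter the feasibility conclusion. That limits the severity. It does not remove the point, because section 4.1.1 carries secondary results into the next trial's sample size.

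**Conclusion.** The point holds in a limited form. Section 4.1 leaves the scale and the handling of outliers open for two positive-valued biomarkers measured in 12 people per role, and its check leads nowhere. If values are right-skewed with proportional change, a within-person log analysis is more precise, by the amounts in the table. Those amounts rest on an assumed distribution, correlation and effect.

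Two stronger conclusions are not supported. The gain is not large whichever t-test is used; much of it depends on the analysis also being paired. And logs are not free: they change the estimand to a ratio of geometric means, need a rule for zero or below-detection values, and lose some power if values are near-symmetric with additive change (65% to 57% at CV 0.3, r 0.6).

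This is a cheap improvement of minor to moderate importance.

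**What to change.** State in section 4.1 that:

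- hair cortisol (T2 v T0) and amylase (post v pre session, using all sessions in a mixed model) are analysed within person on the natural-log scale, separately for adolescents and parents;
- results are reported as geometric mean ratios with 95% confidence intervals;
- zero or below-detection values follow a stated rule;
- no value is removed as an outlier unless the assay failed;
- individual raw values are plotted, and an untransformed within-person analysis is given as a sensitivity check.

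The cost is a few sentences and one extra analysis, with no new data. Readers get ratios in place of differences in pg/mg. The sensitivity analysis shows whether the choice of scale mattered, which covers the case where change is additive.
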